9.17.2. Carbohydrate Deficient Transferrin

Chronic alcohol use causes a transient change in the glycosylation pattern of transferrin, where the relative amounts of disialo- and asialotransferrin (carbohydrate deficient transferrin [CDT]) are increased over the amount of normally glycosylated tetrasialotransferrin. CDT can be used to detect whether someone is a binge drinker or a daily heavy drinker (4 or more drinks a day) ([Fleming, 2004](#)). It can even be used to determine AUD relapse ([Mitchell, 1997](#)). Generally, CDT levels will return to normal within several weeks of abstinence of alcohol use. CDT testing alone is not recommended for general screening for AUD; however, when combined with other assessments (e.g.: gamma-glutamyl transpeptidase [GGT], alanine aminotransferase [ALT], aspartate aminotransferase [AST], mean corpuscular volume [MCV], EtG, and patient self-reporting), clinicians can expect to identify the majority of patients with AUD ([Gough, 2015](#)).

9.17.3. Haematology and Clinical Chemistry

Changes in the reported values of MCV, ALT, AST, and GGT will also be used to monitor for signs of relapse.

10. ASSESSMENT OF SAFETY

Patient safety will be assessed by laboratory assessments (routine haematology, clinical biochemistry, and coagulation), physical examinations, 12-lead ECGs and cardiac telemetry, vital signs (BP, HR, and temperature), and the C-SSRS. AEs and concomitant medications will be recorded from Screening until the patient's last visit. Nasal site reaction will be assessed after dosing.

10.1. Safety Parameters

10.1.1. Demographic/Medical History

A detailed medical history, including concomitant medication, will be obtained at the Screening Visit.

10.1.2. Vital Signs

Vital sign measurements (HR, systolic and diastolic BP) and temperature must be collected at each visit outlined in the Schedule of Events ([Table 1](#)). The baseline will be measured in triplicate within 30 min (+/- 5mins) before dosing, (Triplicate measurements should be obtained as closely as possible in succession, and no more than 2 min apart; temperature does not need to be repeated in triplicate). Predose BP must be within normal range pre dose on dosing day and if not then repeated ~ 1 h later .

Vital signs then taken as single measurements at 10, 20, 30, 40 mins, and then every 30 min (+/- 5mins) from 1 hour post-dose until 4 hours post dose: and when the patient is assessed as ready to be discharged on Day 0, if later than 4 h post dose. BP should be measured in the supine position under standardised conditions. A note should be taken of any movement of the participant during blood pressure measurements. If systolic blood pressure is > 160 mmHg then repeat the measurement. Vital signs from 90 min post-dose onwards will form part of the readiness for discharge questionnaire and can be stopped once the patients are confirmed ready for discharge as per the questionnaire.

10.1.3. Weight and Height

Weight and height must be collected at Screening, Day 0, and Day 84.

10.1.4. Physical Examination

A physical examination will be performed at the Screening Visit and at Days 28, 56, and 84.

Any physical examination findings that qualify as AEs or SAEs must be documented on the appropriate CRF pages.

10.1.5. Electrocardiogram

A 12-lead ECG will be obtained (in triplicate, 2 minutes apart) at Screening to assess eligibility and at the visits outlined in [Table 1](#). Recordings will be made with patients in a supine position; patients will remain in that position for at least 10 min before the ECG is recorded. PR, RR, QRS and QT intervals will be captured. QT interval will be corrected using Fridericia's formula (QTcF). The ECG may be repeated as clinically indicated during the study at the discretion of the Investigator.

10.1.6. Cardiac Telemetry

Cardiac telemetry will be conducted on Day 0 starting approximately 30 minutes before dosing up to 90 minutes post dose and any anomalies reported. The cardiac telemetry may be repeated as clinically indicated during the study at the discretion of the Investigator. Recordings will be stored securely electronically or printed in compressed format on A4 pages; any important abnormalities will be printed in uncompressed form, and commented upon by the Investigator.

10.1.7. Mini-International Neuropsychiatric Interview

A Mini-International Neuropsychiatric Interview (MINI) ([Sheehan, 1998](#)) will be performed for each patient at the Screening Visit.

Positive diagnoses on the MINI will be subject to confirmation by a psychiatrist at a clinical interview.

10.1.8. Columbia-Suicide Severity Rating Scale

Patient suicidal ideation will be assessed at the visits outlined in [Table 1](#) using the C-SSRS ([Posner, 2011](#)). The questionnaire will be administered by the Investigator or an appropriate delegate. The “baseline” questionnaire will be used at Screening, considering activity from the last 12 months, and the “since last visit” questionnaire will be used for subsequent visits.

10.1.9. Reactivation Questionnaire

Epidemiological data and anecdotal reports indicate that the use of 5-MeO-DMT is associated with the potential occurrence of a complex and not well understood phenomenon that has been termed “reactivation” (Ortiz Bernal et al, 2022). Anecdotal reports online do seem to suggest that reactivations tend to occur mainly at night as people are drifting off to sleep, and generally tend to dissipate the longer the time has elapsed from the time they took 5-MeO-DMT. In a broad sense, it appears that reactivations are experienced as transient but intense (Type 1 Hallucinogen Persisting Perception Disorder [HPPD]) and tend to subside days or weeks after 5-MeO-DMT use in most cases, as opposed to persisting over longer periods of time as is the case with HPPD Type 2. More data are needed, therefore the ReAQ was developed for study teams to measure the occurrence, context and emotional valence of potential reactivations. The questionnaire will be completed by a psychiatrist or study physician on paper (Appendix 5 Reactivation questionnaire).

10.1.10. Laboratory Assessments

Blood samples will be collected at the Screening Visit and at the visits outlined in [Table 1](#). Clinical laboratory evaluations will be performed locally. Additional laboratory tests should be performed per standard of care, and significant findings should be reported in the CRF.

10.1.10.1. Haematology

- Haemoglobin
- White blood cell count
- Red blood cell count
- Differential count
- Platelet count
- Mean corpuscular volume (MCV)

10.1.10.2. Clinical Chemistry

- Potassium
- Sodium
- Creatinine
- Gamma-glutamyl transpeptidase (GGT)
- Urea
- Alanine aminotransferase (ALT)
- Aspartate aminotransferase (AST)
- Alkaline phosphatase
- Total bilirubin

10.1.10.3. Coagulation

Coagulation variables to be assessed during the study are prothrombin time, activated partial thromboplastin time, and international normalized ratio.

The results of all local laboratory tests required by this protocol will be provided as a report and included in the patient's medical notes.

Any abnormal laboratory test result considered clinically significant by the site Investigator must be recorded on the appropriate AE page of the CRF and should be followed up as adequate until it has returned to normal or a satisfactory explanation has been provided.

10.1.10.4. Drug Screen

Urine will be tested for drugs of abuse during the Screening Period and before dosing on Day 0 according to the laboratory's SOP. Tests will include amphetamines, cocaine, opiates, cannabis, barbiturates, benzodiazepines, MDMA. Drug testing kits will be used. An Alcohol Breath Test will also be performed pre-dose at D0, and CDT and EtG are performed at screening. The results must be obtained before dosing.

10.1.10.5. Pregnancy Screen

A urine pregnancy test (human chorionic gonadotrophin) will be performed during Screening for WOCBP. Pregnancy testing is also to be performed and results obtained before dosing on Day 0. The results must be negative for the patient to continue in the study.

For female patients whose postmenopausal status is unconfirmed, a blood sample for serum FSH will be obtained at Screening to document postmenopausal status.

10.1.10.6. Nasal Site Reaction

A physician will examine the nostrils for evidence of any local site reaction after dosing.

10.2. Adverse and Serious Adverse Events

10.2.1. Definition of Adverse and Serious Adverse Events

The Investigator is responsible for the detection and documentation of events meeting the criteria and definition of an AE or SAE as provided in this protocol.

Each patient will be instructed to contact the Investigator immediately should they manifest any signs or symptoms they perceive as serious.

10.2.1.1. Adverse Event

An AE is any untoward or unfavourable medical occurrence, including abnormal sign (eg, abnormal physical examination or laboratory finding), symptom, or disease related to the patient's participation in the study, which does not necessarily have a causal relationship with the study drug. AEs should be reported throughout the study, any time after consent until 30 days after dosing, whichever is latest.

Examples of an AE include:

- A new condition detected or diagnosed after participation in the study even though it may have been present prior to the start of the study
- Signs, symptoms, or clinical sequelae of a suspected overdose of a concurrent medication (an overdose per se should not be reported as an AE/SAE)
- Signs or symptoms temporally associated with study participation.

Examples that are NOT an AE include:

- A medical or surgical procedure (e.g., endoscopy, appendectomy); the condition that leads to the procedure is an AE
- Situations where an untoward medical occurrence did not occur (social and/or convenience admission to a hospital).

Investigators should consider an event that leads to an intervention, including withdrawal of drug treatment, dose reduction, or significant additional concomitant therapy, as an AE.

Clinically significant changes in the findings of physical examination, and clinically significant abnormalities in the results of objective tests (e.g. laboratory variables, ECG) may also be considered as AEs. The investigator will use the following criteria when deciding whether to report an abnormal result as an AE. If any of these criteria are met, the investigator will report the result as an AE.

1. The test result is associated with accompanying symptoms.
2. Results of additional diagnostic tests cause concern or necessitate medical intervention.
3. As a consequence of the test result, or the subject is given concomitant treatment.
4. The investigator considers the result to constitute an AE.

10.2.1.2. Serious Adverse Event

An SAE is an AE occurring during any study phase (i.e., baseline, treatment, or follow-up) that fulfils one or more of the following:

- Results in death
- Is immediately life-threatening
- Requires in-patient hospitalization or prolongation of existing hospitalization
- Results in persistent or significant disability or incapacity
- Results in a congenital abnormality or birth defect in the offspring of a study patient

- Other important medical events

NOTE: The term “life-threatening” in the definition of “serious” refers to an event in which the patient was at risk of death at the time of the event. It does not refer to an event that hypothetically might have caused death if it were more severe.

NOTE: In general, “hospitalization” signifies that the patient has been detained (usually involving at least an overnight stay) at the hospital or emergency ward for observation and/or treatment that would not have been appropriate in the physician’s office or outpatient setting.

Complications that occur during hospitalization are AEs. If a complication prolongs hospitalization by at least 1 overnight stay or fulfils any other serious criteria, the event is serious.

When in doubt as to whether “hospitalization” occurred or was necessary, the AE should be considered serious.

Hospitalization for elective treatment of a pre-existing condition that did not worsen from baseline is not considered an AE.

NOTE: The term “disability” means a substantial disruption of a person’s ability to conduct normal life functions. This definition is not intended to include experiences of relatively minor medical significance such as uncomplicated headache, nausea, vomiting, diarrhoea, influenza, or accidental trauma (e.g., sprained ankle) that may interfere with or prevent everyday life functions but do not constitute a substantial disruption.

NOTE: Medical or scientific judgement should be exercised in deciding whether reporting is appropriate in other situations, such as other important medical events that may not be immediately life-threatening or result in death or hospitalization but may jeopardize the patient or may require medical or surgical intervention to prevent one of the other outcomes listed in the above definitions. These should also be considered serious.

Examples of such events are second primary cancers, intensive treatment in an emergency room or at home for allergic bronchospasm, and blood dyscrasias or convulsions that do not result in hospitalization.

All SAEs that occur after any patient has consented to the study, before treatment, during treatment, or within 30 days following the cessation of treatment, whether or not they are related to the study, must be recorded on forms provided by BPL and reported to the Sponsor or its designee within 24 hours of the Investigator becoming aware of the incident.

10.2.2. Relationship to Study Drug

The Investigator should make an assessment of whether the AE is likely to be related to study drug according to the following definitions, taking into consideration temporal relationship of the event to the study procedure and alternative causes, such as natural history of the underlying diseases, concomitant therapy, and other risk factors.

- **Not Related:** An AE for which there is no reasonable temporal association between its onset and administration of the study drug or that can reasonably be explained by other factors, including underlying disease, complications, concomitant drugs, or concurrent treatment.

- **Unlikely Related:** An AE with a temporal relationship to study drug administration that makes a causal relationship improbable, and in which other drugs, chemicals, or underlying disease provide plausible explanations.
- **Possibly Related:** An AE for which there is a reasonable temporal association between its onset and study drug administration and for which other causal factors may not be excluded.
- **Probably Related:** An AE for which there is a reasonable temporal association between its onset and study drug administration and that is at least more likely to be explained by the study drug administration than by any other cause (e.g., underlying disease, complications, concomitant drugs, or concurrent treatment).

There may be situations when an SAE has occurred but the Investigator has minimal information to include in the initial report. However, it is very important that the Investigator always makes an assessment of causality for every event on the initial submission of the SAE. The Investigator may change his/her opinion of causality in light of follow-up information, amending the SAE information accordingly. The causality assessment is one of the criteria used when determining regulatory reporting requirements.

For expedited regulatory reporting purposes, the classification of “Not Related” or “Unlikely Related” will be considered “Unrelated”, meaning that no valid reason exists for suggesting a relationship; classification of “Possibly Related” or “Probably Related” will be considered “Related”, meaning that there is a valid reason, even undetermined, for suspecting a possible cause-and-effect relationship between the study drug and the occurrence of the AE.

10.2.3. Assessment of Severity

The severity of AEs will be graded on a 3-point scale using the following definitions:

- **Mild:** Discomfort noticed but no disruption of normal activity
- **Moderate:** Discomfort sufficient to reduce or affect normal daily activity
- **Severe:** Inability to work or perform normal daily activity

Changes in the severity of an AE will be documented to allow an assessment of the duration of the event at each level of severity to be performed. AEs characterised as intermittent require documentation of onset and duration of each episode.

10.2.4. Recording AEs and SAEs

All SAEs/AEs will be recorded as they are reported, whether spontaneously volunteered or in response to questioning about well-being at study visits. The questioning about SAEs/AEs will cover the current visit as well as the time between the previous and the current visit. All SAEs/AEs occurring after the patient signs the ICF until the end of the Follow-up Visit, or 30 days after dosing the last dose (whichever is latest) must be recorded on the relevant SAE/AE page in the patient’s eCRF, irrespective of severity or whether or not they are considered related to the treatment.

All SAEs/AEs observed by the Investigator or one of his/her clinical collaborators or reported by the patient spontaneously or in response to a direct question will be evaluated by the Investigator.

The nature of each event, date and time (where appropriate) of onset, outcome, severity, and relationship to study procedure should be established. Details of any corrective treatment should be recorded on the appropriate page of the eCRF.

Concomitant medication administered for the treatment of an SAE, at any time, must also be recorded on the SAE report form.

As a consistent method of soliciting AEs, the patient should be asked a nonleading question such as: "How have you felt since participating in the study or since the previous visit?"

Note: The Investigator should record only those SAE or AEs having occurred within the time frame defined above.

When an AE/SAE occurs, it is the responsibility of the Investigator to review all documentation (e.g., hospital progress notes, laboratory and diagnostic reports) relative to the event. The Investigator will attempt to establish a diagnosis of the event based on signs, symptoms, and/or other clinical information. In such cases, the diagnosis should be documented as the AE/SAE and not the individual signs/symptoms.

The Investigator or designee will then record all relevant information regarding the AE/SAE in the eCRF. Note that the eCRF should not be used to report SAEs. This should be done using the paper SAE Report form, to the sponsor or designee within the required 24 hours of becoming aware of the incident.

10.2.5. Follow-up of AEs and SAEs and Assessment of Outcome

After the initial AE/SAE report, the Investigator is required to proactively follow each patient and provide further information on the patient's condition.

All AEs and SAEs documented at a previous visit/contact and designated as not recovered/not resolved or recovering/resolving will be reviewed at subsequent visits/contacts.

Investigators will follow up patients

- With at least 1 SAE or patients withdrawn from the study due to an AE, until the event has resolved, subsided, or stabilised; the event is otherwise explained; or the patient is lost to follow-up
- In the case of other nonserious AEs, patients will be followed until they complete the study or are lost to follow-up
- The Investigator should not conclude that the patient is lost to follow-up earlier than 30 days after discontinuation of study drug

Clinically significant laboratory abnormalities will be followed up until they have returned to normal or a satisfactory explanation has been provided. Additional information (including but not limited to laboratory results) relative to the subsequent course of such an abnormality noted for any patient must be made available to the Investigator. If a clinically significant laboratory abnormality is reported as an AE, the Investigator will determine the severity and relatedness of the event.

The outcome of any nonserious AE or any SAE reported during the entire study will be assessed as follows:

- Recovered/resolved

- Not recovered/not resolved
- Recovering/resolving
- Recovered with sequelae/resolved with sequelae
- Fatal (SAEs only)

10.2.6. Pregnancy and Pregnancy Follow-up

If, during the study, the Investigator becomes aware of a pregnancy in a patient or their partner, it must be reported to the Sponsor's pharmacovigilance delegate details below using the paper pregnancy form, immediately (within 24 hours of the Investigator's awareness). Pregnancy in itself is not regarded as an AE unless there is a suspicion that an investigational product may have interfered with the effectiveness of a contraceptive medication.

Provided the patient (or their partner) consents, the Investigator will follow the pregnancy. The outcome of all pregnancies (spontaneous miscarriage, elective termination, normal birth, or congenital abnormality) must be followed up and documented even if the patient was discontinued from the study. All reports of congenital abnormalities/birth defects are SAEs.

Spontaneous miscarriages should also be reported and handled as SAEs. Elective abortions without complications should not be handled as AEs.

10.2.7. Adverse Events of Special Situations

The following AESS events should be reported in an expedited manner (within 24 hours of the Investigator's awareness) to the Sponsor's pharmacovigilance delegate, using the SAE process, regardless of severity.

- Any exposure to study drug through breastfeeding
- AEs associated with study drug overdose or medication error
- AEs associated with study drug abuse, misuse, overuse

10.2.8. AEs of Special Interest (AESI)

An AE of special interest (AESI) is an AE (serious or nonserious) of scientific and medical concern specific to study medication, for which ongoing monitoring and immediate notification by the investigator to the Sponsor is required. Such AESIs may require further investigation to characterize and understand them. AESIs should be reported to the Sponsor's pharmacovigilance delegate as per the SAE reporting process for the study (see Section 10.3).

The AESIs indicative of the below will be monitored for this study.

- AEs indicative of abuse potential,
- Significant suicidality ideation, defined as a response of "Yes" on Item 4 (active suicidal ideation with some intent to act, without specific plan) or Item 5 (active suicidal ideation with specific plan and intent) for suicidal ideation on the C-SSRS or suicidal behaviour.

AEs indicative of abuse potential include the following for events, unless they are observed before dosing:

- Euphoric mood
- Elevated mood
- Feeling abnormal
- Feeling drunk
- Feeling of relaxation
- Dizziness
- Abnormal thinking
- Hallucinations
- Inappropriate affect
- Somnolence
- Mood disorders and disturbances
- Psychosis
- Aggression
- Confusion and disorientation

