11. History of intolerance to 5-MeO-DMT, dimethyltryptamine (DMT), or related compounds
12. Any nasal obstruction, blockage, or symptoms of congestion
13. Any personal or family history of malignant hyperthermia

14. Disposition judged by the Investigator (or delegate) to be incompatible with establishment of rapport with study team and/or safe exposure to BPL-003
15. Presence of acute or chronic illness or infection or history of chronic illness or infection sufficient to invalidate the patient's participation in the study or make it unnecessarily hazardous
16. Presence or history of severe adverse reaction to any drug or drug excipient
17. Female patients who are pregnant or lactating or are of childbearing potential and not willing to use adequate forms of contraception during the study and for 1 month after completion of the study as described in the protocol
18. Male patients who are sexually active and not willing to use adequate forms of contraception during the study or for 1 month after completion of the study as described in the protocol
19. Patients who have taken part in a clinical research study in the last 4 weeks, whether or not they received an investigational medicinal product as part of that research study
20. Current criminal justice involvement with legal proceedings, which in the opinion of the Investigator means the participant may fail to complete the study protocol due to inability to complete study visits with the study site team
21. Unable to communicate in English to a level required to accept standard care and psychological intervention
22. Patients who, in the opinion of the Investigator, are not suitable to participate in the study for any other reason not mentioned in the entry criteria

Psychiatric Exclusion Criteria:

23. Personal or first-degree family history of schizophrenia, bipolar disorder, psychotic disorder (unless substance induced or due to a medical condition), delusional disorder, paranoid disorder or schizoaffective disorder, as defined by DSM-5. Personal history determined by medical records and positive diagnoses on the Mini-International Neuropsychiatric Interview (MINI) to be confirmed by the Investigator
24. Any major psychiatric disorders, with the exception of mild or moderate anxiety and/or depression, as determined by a MINI and confirmed by the Investigator
25. A clinical diagnosis of post-traumatic stress disorder (as determined by MINI)

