11.7.1.1. Adverse Events and Serious Adverse Events

AEs will be coded using the version of the Medical Dictionary for Regulatory Activities (MedDRA) current at the time of database lock.

All AEs will be listed.

A TEAE is an AE that emerges during treatment (having been absent before treatment) or that worsens after treatment ([International Council for Harmonisation, 1998](#)). The number of patients with at least one TEAE will be tabulated by actual treatment and MedDRA system organ class and preferred term. For each of the following, the number of TEAEs and the number of patients with TEAEs will be summarised as follows:

- TEAEs by system organ class and preferred term
- Drug-related TEAEs by system organ class and preferred term

Patients with more than one TEAE will be counted only once, at the maximum causality, for each system organ class and preferred term. AEs with missing severity and/or causality will be treated as severe and possibly related, respectively.

AEs leading to withdrawal, deaths, and other SAEs will be listed separately (fatal events will be listed separately from nonfatal events).

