14.2 Adverse events

AEs will be coded using the version of the MedDRA which is current at the time of database lock (version 27.0 or higher).

All AEs will be listed.

The number of patients with at least one treatment-emergent adverse event (TEAE) per treatment will be tabulated by actual treatment and MedDRA system organ class. A TEAE is defined as an event emerging during treatment (having been absent pre-treatment) or that worsens after treatment¹.

For each of the following, the number of TEAEs and the number of patients with TEAEs will be summarised:

- TEAEs, by system organ class and preferred term
- TEAEs, by system organ class and preferred term and by severity
- Drug-related (“probably” or “possibly” as recorded by the investigator) TEAEs, by system organ class and preferred term.

In addition, a summary of TEAEs by day of onset (Day 0, Days 1-6 and Day 7 or later) will be produced.

Patients with more than one TEAE will be counted only once, at the greatest severity or causality, for each system organ class/preferred term. Multiple TEAEs in a patient will be counted once per system organ class and preferred term. AEs with missing severity and/or causality will be treated as severe and possibly related, respectively.

Summaries will be sorted by system organ class and decreasing total incidence of preferred term.

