14.6 Adverse events of special interest (AESI)

AESIs will be listed separately.

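### The abuse-potential AESI definition drops listed events seen before dosing with no exception for worsening, so a non-serious event that worsens after BPL-003 can be a TEAE but not an AESI

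*Protocol*

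**What the plan says.** Protocol 10.2.8 has two AESI categories: significant suicidality, and AEs indicative of abuse potential. For the second it gives a list of events, among them dizziness, somnolence and "Mood disorders and disturbances", introduced by the sentence "AEs indicative of abuse potential include the following for events, unless they are observed before dosing". AESIs need prompt notification to the sponsor and go through the SAE reporting route.

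For treatment emergence, protocol 11.7.1.1 says "A TEAE is an AE that emerges during treatment (having been absent before treatment) or that worsens after treatment". SAP 14.2 agrees: "A TEAE is defined as an event emerging during treatment (having been absent pre-treatment) or that worsens after treatment".

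On recording, protocol 10.2.3 says "Changes in the severity of an AE will be documented", and protocol 10.2.4 requires "All SAEs/AEs occurring after the patient signs the ICF until the end of the Follow-up Visit" to be entered in the eCRF, so the AE record opens before Day 0. Protocol 5.2.2.2 excludes major psychiatric disorders "with the exception of mild or moderate anxiety and/or depression".

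The SAP's whole treatment of AESIs is section 14.6, "AESIs will be listed separately", which is delivered as Listing 16.2.7.5.

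**The concern.** Two rules that sort the same post-dose events use different tests. The TEAE rule removes symptoms that were there before dosing and stayed the same, but keeps those that got worse. The AESI rule removes anything seen before dosing, whatever happens afterwards.

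The situation can arise in this trial. Screening may start 28 days before dosing, AEs are recorded throughout that time, patients are limiting their alcohol intake before Day 0, and mild or moderate anxiety or depression is allowed at entry. At stake is whether an aggravation of such a symptom after a psychoactive drug reaches the sponsor as an event of special interest, and whether it appears in the one output the SAP sets aside for those events.

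**Working it through.** No arithmetic applies: the plan gives no figure here and the point concerns an event definition. The check sets the two rules side by side for a non-serious event on the 10.2.8 list.

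| Course of the listed event | TEAE (protocol 11.7.1.1, SAP 14.2) | Abuse-potential AESI (protocol 10.2.8, plain wording) |
|---|---|---|
| (a) Absent before dosing, appears after | Yes | Yes |
| (b) Present before dosing, unchanged after | No | No |
| (c) Present before dosing, worse after | Yes | No |

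The rules agree in (a) and (b) and part in (c).

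Three further questions decide whether (c) matters in practice.

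1. *Does another passage bring worsened events back in?* None does. SAP 14.6 gives no derivation rule, and the AE listing template simply carries an AESI flag.

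2. *Does a worsening open a new AE, so that the pre-dose exclusion no longer applies?* No passage says so. Protocol 10.2.3 documents a severity change so that the time spent at each severity level of the AE can be assessed, which points to one continuing AE. That AE was observed before dosing. A site could still open a new record for the worsening and flag it. The protocol does not settle this, and the study has two sites (protocol 4.1), so the same event could be classified in two ways.

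3. *What does a case (c) event lose?* It loses the AESI notification and its line in Listing 16.2.7.5. It keeps its place in the TEAE tables by system organ class, preferred term and severity. It also stays in the all-AE listing (16.2.7.1), whose template shows severity and treatment emergence, and it still counts in the primary percentage of patients with TEAEs.

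Size: up to 12 patients are planned, so each affected patient would be at least 1/12 = 8.3% of the sample. The documents give neither the frequency of listed symptoms before Day 0 nor the chance that one worsens, so the number affected cannot be derived.

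**The case against.** The best defence is that a TEAE and an abuse-potential AESI serve different purposes and nothing requires them to match. Filtering out what was present before the drug is a recognisable way to isolate signals such as euphoric mood or feeling drunk. The version 7.0 summary of changes presents the clause as intended. In a study of at most 12 patients with no hypothesis test, the full AE listing can be read line by line. Psychiatric worsening is also followed through the C-SSRS, MADRS, CGIS and ReAQ.

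Much of this stands, and it limits the point to one notification and one listing. It does not justify ignoring worsening: the TEAE definition already filters unchanged baseline symptoms without discarding aggravated ones. It could also be said that the list is introduced as inclusive rather than exhaustive. But if a worsened pre-dose dizziness could enter that way, the exclusion would have no effect.

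A reader might infer four stronger things that the documents do not support.

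- *Such patients can never have an AESI.* The suicidality category is a separate bullet without the pre-dose exclusion, so C-SSRS Item 4 or 5 ideation, or suicidal behaviour, still qualifies. The same patient can also have an AESI for any other listed term. Serious worsening is reported as an SAE under protocol 10.3.
- *Everyone with anxiety or depression at entry is caught.* These conditions may sit in medical history, which SAP 13.3 lists apart from AEs. Whether a history entry counts as observed before dosing is not stated.
- *A fresh post-dose episode of a symptom that had resolved is also lost.* That needs the exclusion to apply to the type of event rather than the occurrence. The text does not say which.
- *A set number of patients is affected.* Multiplying an assumed symptom prevalence by 12 has no source in the documents. It would also count everyone with a pre-dose symptom rather than those whose symptom worsens.

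**Conclusion.** The point holds as a gap between two definitions. It rests on the plain wording of 10.2.8 and on a severity change staying within the same AE, as 10.2.3 suggests. If a site instead recorded each worsening as a new AE, that site might flag it, and the problem would become inconsistency between sites rather than uniform omission.

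This is a stated rule, not missing detail. Its consequences are narrow: no endpoint changes and no safety data are lost from the full listings. It is worth correcting because safety is the primary objective and the correction is cheap. It does not call the primary safety results into question.

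**What to change.** In protocol 10.2.8, replace the pre-dose exclusion at the end of the sentence introducing the list with a positive rule: listed events *that start, recur or worsen in severity after dosing*. This follows the TEAE definition on worsening and also settles how recurrences are handled. State the same rule in SAP 14.6 and apply it to Listing 16.2.7.5.

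The cost is one sentence in each document and a few more AESI notifications. Unchanged baseline symptoms would still be filtered out, and no endpoint, TEAE table or treatment rule is affected.
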